5. STATISTICAL CONSIDERATIONS

5.1 Interim Analysis

No interim analysis is planned for this study.

5.2 Final Analysis

The final planned analysis identified in this SAP will be performed by IQVIA Biostatistics following Baxalta's (now part of Shire) authorization of this SAP and Database Lock.

The final analysis will be performed on a clean database:

- All outstanding data issues and queries resolved.
- All irresolvable data issues documented in the Data Handling Report (DHR) from Data Management.
- All coding of medications and AEs completed.
- SAE reconciliation completed.
- Flagging of clinically significant changes in vitals signs by Baxalta (now part of Shire) completed.
- All reconciliation of vendor data with eCRF data completed successfully.

It should be noted that all verbatim text from the eCRF presented in any outputs, will be presented verbatim with no manual hard coding corrections for such data.

5.3 Reference Start Date, Surgery Day and Observation Days

5.3.1 Reference Start Date

Reference start date is defined as the day of the subject's first BAX 855 PK-guided prophylactic infusion, after enrolment in the 261303 protocol (henceforth referred to as the PROPEL study) and will be referred to as ObsDay 1. Subjects who discontinue study participation prior to receiving any BAX 855 prophylactic administration in the PROPEL study are not to have a reference start date.

5.3.2 Surgery Day

Surgery day (SDay) is a relative study day, calculated per surgical procedure for each subject as applicable. The day on which the subject receives pre-surgical loading dose is defined as SDay 1 for each respective surgery. SDay will then increase for every day after SDay 1 until the day before the subject resumes PK-guided prophylaxis in the PROPEL study.

To distinguish between SDays of different surgeries per subject, an additional variable will be assigned, indicating a specific surgery as the *i*'th chronologic surgery for the subject.

$$\text{Surgery Day} = (\text{Date of Event} - \text{Date of SDay 1})$$

Where date of event is any surgery related assessment or measurement performed.

For example, consider a subject that had two surgeries during the study and received pre-surgical loading dose on the same day as the surgery procedure. For the 1st surgery, the subject resumed regular PK-guided prophylaxis 3 days after the procedure and for the 2nd surgery, 4 days after the procedure. The subject would then have SDay running from 1 to 2 for the 1st surgery and SDay running from 1 to 3 for the 2nd surgery.

Surgery days/periods will be excluded for efficacy analyses purposes as if the subject left the study for surgery and returned to the study once regular PK-guided prophylaxis was resumed (as was the actual case for the 261302 study).

5.3.3 Observation Day

ObsDay is calculated from the Reference Start Date, and will be used to present the relative start and stop day of assessments and events not related to surgery.

- If the date of the event is prior to the Reference Start Date then:

$$\text{ObsDay} = (\text{Date of Event} - \text{Reference Start Date})$$

- If the date of the event is on or after the reference start date then:
 - If a subject has no surgeries between Reference Start Date and the date of event then:

$$ObsDay = (Date\ of\ Event - Reference\ Start\ Date) + 1$$

- If a subject has one or more surgeries between reference start date and the date of event then:

$$ObsDay = (Date\ of\ Event - Reference\ Start\ Date) + 1 - \\ (Total\ Number\ of\ SDays\ preceding\ Date\ of\ Event)$$

In the situation where the assessment/event date is partial or missing, observation day and corresponding durations will not be calculated.

5.4 Observation Periods and Annualized Bleeding Rate

Two types of observation period will be defined for use within the analysis and reporting of this study namely the observation period of efficacy (OPE), and the extended observation period of efficacy (eOPE).

5.4.1 Observation Period of Efficacy

- The observation period for efficacy (OPE) measured in days, is calculated as:

$$OPE(days) = Observation\ day\ of\ last\ BAX\ 855\ Prophylactic \\ /IR\ Treatment + Last\ Assigned\ Infusion\ Frequency\ (days)$$

Where last assigned infusion frequency is the last dosing frequency assigned to the subject under a dose change or, in the absence of any dose changes, it is the assigned dose frequency at the start of the study.

- The OPE in (years) is calculated from the OPE (days) as:

$$OPE(years) = \frac{OPE(days)}{365.2425}$$

- The OPE (weeks) is calculated from the OPE (days) as:

$$OPE(weeks) = \frac{OPE(days)}{7}$$

- The OPE (months) is calculated from the OPE (years) as:

$$OPE(months) = OPE(years) \times 12$$

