9.3 Withdrawal and Discontinuation

Any subject may voluntarily withdraw (i.e., reduce the degree of participation in the study) consent for continued participation and data collection. The reason for withdrawal will be recorded on the End of Study CRF. Assessments to be performed at the termination visit (including in cases of withdrawal or discontinuation) are described in Section 10.6 and Section 21.3.

Discontinuation (i.e., complete withdrawal from study participation) may be due to dropout (i.e., active discontinuation by subject) or loss to follow-up (i.e., discontinuation by subject without notice or action). Additionally, the investigator and sponsor have the discretion to discontinue any subject from the study if, in their judgment, continued participation would pose an unacceptable risk for the subject.

Subjects also will be withdrawn from treatment or discontinued from further study participation for the following reasons:

- The subject develops a confirmed high responder inhibitory antibody to FVIII (>5 BU by Nijmegen modification of the Bethesda assay) or a low responder inhibitory antibody (≤ 5 BU but ≥ 0.6 BU) that cannot be managed by the protocol-required prophylactic dosing.
- The subject experiences a severe anaphylactic reaction to BAX 855
- The subject requires therapy with another pegylated product (e.g., PEG-Interferon)
- The subject frequently misses administration of IP (misses more than 30% of planned prophylactic doses within any 3-month period)
- The subject is non-compliant with study procedures, in the opinion of the investigator and/or sponsor
- The subject uses his/her usual FVIII therapy following the baseline infusion
- The subject requires major emergency surgery during this study
- The subject experiences a life-threatening bleeding episode (e.g., any gastrointestinal hemorrhage or intracranial hemorrhage) requiring the use of a FVIII concentrate other than BAX 855
- The subject experiences severe trauma requiring extensive FVIII replacement therapy other than BAX 855

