14.4 Methods of Analysis

14.4.1 Primary Outcome Measure

The proportion of subjects with ABR = 0 in the 2 prophylaxis treatment regimens in the second 6 months period will be compared using a chi-square test with continuity correction at a 2-sided 5% level of significance.

The null hypotheses of no difference between the prophylactic regimens will be tested against a 2-sided alternative.

The observation period for the primary endpoint will be the second 6 months of prophylaxis (Day 183 to Day 364). If the subject undergoes a surgical procedure the observation period is interrupted starting from the presurgical loading dose until the subject resumes his previous prophylactic treatment regimen, or until rehabilitation or any other surgery specific postoperative measures have been completed, whichever occurs last.

Data analyses will follow the intent-to-treat principle, i.e., bleedings observed in the observation period will be used in the analyses irrespective of compliance with the treatment regimen of the protocol. Only if a subject refuses to provide any bleeding data, the multiple imputations (MI) technique will be used to handle observation periods shorter than 6 months, i.e., 182 days, as follows.

For subjects who terminated before Day 364 and refuse to provide data on bleeds, bleeds will be imputed for the unobserved period from a Poisson random variate. The subject specific Poisson parameter will be determined from estimating a negative binomial model for the bleed rate in the unobserved period with stratum, age, race as well as the number of bleeds from Day 92 to the end of the observed period of the subject as covariates in all subjects of the same Study Arm. For subjects with more than 21 weeks in the observation period, the number of bleeds occurring at a later time in other subjects might be very low or even zero. To avoid estimating from an unstable model, the negative binomial model will be for the number of bleed up to Day 329 with covariates of stratum, age, race and number of bleeds observed from Day 92 to Day 329. At least 1000 imputation datasets will be generated. The chi-squared test statistics with continuity correction and its standard error will be used to compare the 2 study arms in each imputation dataset and the multiple imputations techniques will be used to derive an overall estimate with 2-sided 95% CIs.

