5.4.2 Extended Observation Period of Efficacy

The protocol requires that for subjects that did not complete the full 364 observation days, this study should also include any post-discontinuation (post-PROPEL), bleed information provided by either the subject, or from another BAX 855 study, to augment the bleed data for the subject's missing observation period in PROPEL. To facilitate the use of this post-PROPEL data in the efficacy analysis, the extended observation period of efficacy (eOPE) is defined:

- The eOPE measured in days, is calculated as:

$$eOPE(days) = OPE(days) + (Imputation\ Start\ Date - Stop\ Date\ of\ post-PROPEL\ bleed\ data)$$

Where Stop Date of post-PROPEL bleed data is defined as the minimum of:

- Date corresponding to subject's ObsDay 364 in the PROPEL study.
- Actual recorded date of the last bleed data provided for the subject as post-PROPEL bleed data.

Imputation start date is defined as the maximum of:

- The day immediately following the date corresponding to OPE (days).
- The day immediately following the stop date of post-PROPEL bleed data.
- Date corresponding to subject's ObsDay 183.

- The eOPE in (years) is calculated from the eOPE (days) as:

$$eOPE(years) = \frac{eOPE(days)}{365.2425}$$

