5.5.1 Annualized Bleeding Rate

For all subjects who prematurely discontinued from the study (i.e., before ObsDay 364), and who refuse to provide data on bleeds for the remaining time till ObsDay 364, the number of bleeds (and hence the ABR), will be imputed for the second 6-month period, using Multiple Imputation techniques as described below. The ABR for a subject is calculated as the number of bleeds divided by the observation period under consideration (expressed in years).

The number of bleeds during the missing observation period in PROPEL, will be imputed for subjects taking into account, additional post-PROPEL bleeding information that is provided for the subject. Post-PROPEL bleeding information obtained for a subject (either by the subject or from another BAX 855 study), will be treated as if observed within PROPEL before the imputation procedures.

For simplicity, the imputation process is described below for a single subject (since the imputation will be performed on a subject specific basis), focussing on the period of interest for the primary endpoint (2nd 6-month period). The imputation process is described in step-by-step manner.

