5.5.1.1 Primary Endpoint Imputation

The unobserved period (which is subject specific), is defined as the subject's missing observation period in PROPEL for which there is no post-PROPEL bleed information provided.

Step1: Fitting the model

- A subject specific Negative Binomial model will be fitted. The dependent variable (left-side of the model equation), is the number of bleeds in the subject's unobserved period after ObsDay 182, taken from all subjects in the same treatment arm (low level or high level), as the subject being imputed. The offset will be the logarithm of the duration (in days), of the unobserved period for the subject (LUP). Covariates (model variables) will be stratum category, race, age at baseline and total number of bleeds observed per subject (OB), calculated for all subjects in the same treatment group of the subject for imputation.

- It is desired to avoid using bleeds in the endmost observation period as part of the covariates since the number of bleeds observed in other subjects at that time might be very low or even zero. Therefore OB, is measured in the range from ObsDay 92 up to the minimum of:
 - Last ObsDay for subject being imputed.
 - ObsDay 329.
- The following example SAS[®] code can be utilized:

```
Proc Genmod Data = <Dataset>;  
  Class <Stratn> <Racen>;  
  Model <UB> = <Stratn> <Racen> <BAge> <OB> / Dist = Negbin  
    Offset = <LUP> Link = log;  
  ODS Output ParameterEstimates = <Outdata>  
Run ;
```

Where <Dataset> represents the input dataset containing all subjects in the same treatment arm as the subject being imputed, who have at least the same amount of ObsDays as the subject being imputed. <UB> represents the number of bleeds during the subject's unobserved period (up to the maximum of ObsDay 329), <Stratn> is the numeric stratum category, <Racen> the numeric race category, <BAge> the age at baseline, <OB> and <LUP> as defined above and <OutData> the output dataset containing the parameter estimates.

Step2: Predicting the Poisson Parameter and Imputing with it

- The subject-specific Poisson parameter will be predicted from the above model fitting results by using the predicted mean number of bleeds during the subject's unobserved period (Mu) as the prediction for the Poisson parameter.
- The number of bleeds for the subject to be imputed, will be for the "imputation period" (days), where the imputation period is defined as:

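### The SAP starts imputing bleeds after the last prophylactic infusion plus one interval, not after the last day with bleed data, so some observed days are imputed as if missing

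*SAP*

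**What the plan says.** Protocol 14.4.1 sets the primary observation period by calendar, Day 183 to Day 364, and states that "bleedings observed in the observation period will be used in the analyses irrespective of compliance with the treatment regimen of the protocol". Imputation is a fallback: "Only if a subject refuses to provide any bleeding data, the multiple imputations (MI) technique will be used to handle observation periods" shorter than six months, and then only for the unobserved part. Protocol 10.6 adds that data gathered up to discontinuation enter the analysis.

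SAP 5.4.1 introduces a different clock. "The observation period for efficacy (OPE) measured in days, is calculated as" the observation day of the last prophylactic or incremental-recovery (IR) infusion plus the last assigned infusion interval. Diary entries, infusions given for bleeds and the discontinuation date play no part.

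SAP 5.4.2 sets the imputation start at the latest of three dates: the day after OPE ends ("The day immediately following the date corresponding to OPE (days")), the day after any post-PROPEL bleed data stop, or ObsDay 183. SAP 5.5.1.1 Step 2 uses that start date for the imputation period.

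The group to be imputed is limited in SAP 5.5.1: "For all subjects who prematurely discontinued from the study (i.e., before ObsDay 364), and who refuse to provide data on bleeds". SAP 5.5.1.1 describes the unobserved period as the "missing observation period in PROPEL for which there is no post-PROPEL bleed information provided", without saying whether a day is missing because it lies after OPE or because no bleed data exist for it.

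**The concern.** A subject can stop prophylactic infusions and still report bleeds until leaving the study. Days between the end of OPE and the last in-study contact are neither inside OPE nor post-PROPEL. If no post-PROPEL data follow, those in-study days fall inside the imputation period although they were observed. That contradicts the protocol's rule that only unobserved time is imputed.

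The primary endpoint is whether any bleed occurred in the second six months, so one imputed bleed turns a bleed-free subject into a subject with a bleed. The SAP is also inconsistent about where observation ends. The observed-bleed covariate (OB) and the observed count in Step 3 are not tied to OPE, whereas the imputation start and the negative binomial offset are.

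**Working it through.** **Planning figure.** The disputed rule has no stated figure, so I first checked the planning rates used below. Inputs from Protocol 14.1.1 and SAP 2.3: 40% and 70% bleed-free, two-sided 5%, 80% power.

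- Without correction: n = [1.96√(2×0.55×0.45) + 0.8416√(0.4×0.6 + 0.7×0.3)]² / 0.30² = 42.0.
- With continuity correction: n = (42.0/4)[1 + √(1 + 4/(42.0×0.30))]² = 48.4.

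The stated 48 per arm is reproduced with the continuity correction; power at 48 is 79.6%.

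**Where observation ends, rule by rule.**

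| Place | Observation runs to |
|---|---|
| Protocol 14.4.1 and 10.6 | Last day with bleed data, up to Day 364 |
| SAP 5.4.1, 5.4.2 and 5.5.1.1 Step 2 (imputation period) | Last prophylactic/IR infusion plus interval, unless post-PROPEL data or ObsDay 183 is later |
| SAP 5.5.1.1 Steps 1 and 2 (OB) | The subject's last ObsDay, capped at 329 in Step 1; not linked to OPE |
| SAP 5.5.1.1 Step 3 (observed count) | All observed bleeds after ObsDay 182 |
| SAP 7.1.2 (negative binomial offset) | End of OPE |

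**Chance of a spurious bleed.** Assume Poisson bleeding at the rates implied by the planning figures over 182 days:

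- Low arm: −ln(0.4)/182 = 0.00503 per day.
- High arm: −ln(0.7)/182 = 0.00196 per day.

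For a subject observed bleed-free through a gap of g days, the chance that imputation adds at least one bleed there is 1 − exp(−rate × g).

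| Gap (days) | Low arm | High arm |
|---|---|---|
| 7 | 3.5% | 1.4% |
| 14 | 6.8% | 2.7% |
| 28 | 13.1% | 5.3% |
| 56 | 24.6% | 10.4% |
| 91 | 36.8% | 16.3% |

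**Effect on the arm proportions at the upper bound.** Dropout close to 10% of 58 per arm is 5.8, so at most about 6 affected. Assume a 28-day gap with bleeding at ten times the low-arm rate; the factor comes from the prophylaxis/on-demand ratio of 0.10 in Protocol 6.4.2. Per affected subject:

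- Bleed-free outside the gap: 0.4^(154/182) = 0.461 and 0.7^(154/182) = 0.739.
- Truly bleed-free in the gap: exp(−28 × 0.0503) = 0.244.
- Imputed bleed-free in the gap: 1 − 0.131 = 0.869 and 1 − 0.053 = 0.947.

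The protocol's rule multiplies the first two terms. Step 3 as written multiplies all three. Truncating observed bleeds to OPE multiplies the first and third. The arm proportion is (52p + 6q)/58, with p = 0.4 or 0.7 and q the per-subject value.

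| Reading | q low / high | Arm low / high | Difference (points) |
|---|---|---|---|
| Protocol | 0.112 / 0.181 | 37.0% / 64.6% | 27.6 |
| SAP Step 3 as written | 0.098 / 0.171 | 36.9% / 64.5% | 27.7 |
| Truncated to OPE | 0.400 / 0.700 | 40.0% / 70.0% | 30.0 |

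**Range.** The Step 3 effect is small here because most affected subjects would already have bled in the gap. If the gap rate were only the arm's own planning rate, the protocol's q would be 0.400 and 0.700. Step 3 would then lower the arm proportions by (6/58)(0.400 × 0.131) = 0.5 point and (6/58)(0.700 × 0.053) = 0.4 point, and truncation would change nothing.

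**The case against.** A reader might infer that recorded bleeds are erased and replaced by on-prophylaxis draws, biasing the primary endpoint toward bleed-free. The text does not say that. Step 3 adds the imputed count to every observed bleed after ObsDay 182, and SAP 7.1.2 repeats that recorded bleeds count whatever the compliance. The observation period in that passage is most naturally the calendar one. As written, the error runs the other way. Erasure would need a programmer to equate that phrase with OPE; the SAP's loose use of the term permits this but does not instruct it.

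A reader might also infer that everyone who stops infusing is affected. That does not hold either:

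- Imputation applies only to early discontinuers who refuse later data.
- Post-PROPEL data move the start date past the gap.
- Gaps before ObsDay 183 do not touch the primary endpoint.
- Protocol 21.2 and 21.3 schedule a prophylactic infusion at the termination visit for discontinuers too; if given, it extends OPE beyond that visit.

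Nor does the withdrawal rule in Protocol 9.3 ("misses more than 30% of planned prophylactic doses within any 3-month period") build in a gap. Thirty percent of 91 days is 27 days only if the misses are consecutive and fall at the end; scattered misses leave no trailing gap.

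Finally, a donor set "taken from all subjects in the same treatment arm (low level or high level), as the subject being imputed" follows the protocol's own imputation rule, and analyses with inflated rates are planned.

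These points limit the reach and size, but they do not remove the start-date error. The termination visit is only to be attempted, so an infusion there is not assured. Two subjects with identical diaries could get different imputation windows because one was infused at exit. The inflated rates change how many bleeds are drawn, not which days they are drawn for.

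**Conclusion.** The concern holds in a narrow form. The imputation start is tied to the last prophylactic or IR infusion when the protocol requires it to follow the last observed day. For the subjects who meet all the conditions, observed days are imputed.

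As written, the consequence is occasional spurious bleeds and a slightly lower bleed-free proportion. At the upper bound of about 6 per arm with a 28-day gap, that is about 0.1 point at a tenfold off-prophylaxis rate, and about half a point if the gap rate is the arm's own. If observed bleeds were cut at OPE, the proportions would instead rise by about 3 points (low arm) and 5 points (high arm) at the tenfold rate. The direction of bias in the primary endpoint therefore depends on a choice that the SAP leaves open.

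The documents give neither the number affected nor the gap length. The Poisson form, the 28 days and the tenfold rate are assumptions, and the true number may be zero.

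A related mismatch is not confined to those who refuse data. The negative binomial models in SAP 7.1.2 use log(OPE) as the offset, so any bleed counted after OPE has no matching exposure time.

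**What to change.** Define the end of bleed observation as the last date for which bleed status is known, capped at ObsDay 364. That date is the latest of diary review, termination visit or other last in-study contact, and post-PROPEL data. It should rest on a review or contact: the diary records events, so a day without an entry does not by itself show that the subject was bleed-free.

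Start imputation the next day. Use the same date for the observed bleed count, the OB covariate and the negative binomial offset, and state that the unobserved period in SAP 5.5.1.1 begins after it. Keep the infusion-based OPE for exposure and compliance tables.

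The cost is a wording change in SAP 5.4, 5.5.1 and 7.1.2, one derived date per subject, and the matching program changes. The visit, diary and follow-up information is already collected, so no new data are needed.

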5.4.2 Extended Observation Period of Efficacy

The protocol requires that for subjects that did not complete the full 364 observation days, this study should also include any post-discontinuation (post-PROPEL), bleed information provided by either the subject, or from another BAX 855 study, to augment the bleed data for the subject's missing observation period in PROPEL. To facilitate the use of this post-PROPEL data in the efficacy analysis, the extended observation period of efficacy (eOPE) is defined:

- The eOPE measured in days, is calculated as:

$$eOPE(days) = OPE(days) + (Imputation\ Start\ Date - Stop\ Date\ of\ post-PROPEL\ bleed\ data)$$

Where Stop Date of post-PROPEL bleed data is defined as the minimum of:

- Date corresponding to subject's ObsDay 364 in the PROPEL study.
- Actual recorded date of the last bleed data provided for the subject as post-PROPEL bleed data.

Imputation start date is defined as the maximum of:

- The day immediately following the date corresponding to OPE (days).
- The day immediately following the stop date of post-PROPEL bleed data.
- Date corresponding to subject's ObsDay 183.

- The eOPE in (years) is calculated from the eOPE (days) as:

$$eOPE(years) = \frac{eOPE(days)}{365.2425}$$

